## 5.4 Recruitment and informed consent/objection

5.4.1	Retrospective study (tick all that apply)	
	 Not applicable ( see section 5.2.2 )	
	 Data will be copied from (electronic) patient records (e.g. 'EPD UMCG')	
	 Data/biomaterials will be obtained from an already existing internal or external (UMCG/non-UMCG) bio- or databank (see Section 1. Study organization). Data/biomaterials will be obtained from the 'de novo' biobank Acutelines.	
	 Data/biomaterials will be obtained from a previous study ('FAIR data' - internal/external; see Section 1. Study organization).	
5.4.3 Objection (Registry)		
in case one or more participants will not be asked informed consent, the objection registry will be checked for these participants and the data from those who objected will be excluded from the analyses.		NA
All participants will be asked informed consent (Acutelines). The objection registry will be checked prior to the study to see if patients have withdrawn consent between enrollment and start of the study.		
5.4.4 Informed consent (IC): access to identifiable participant data		
in case one or more study team members will have access to direct/indirect identifiable participant data, informed consent will be/has been obtained for this access.		YES
5.4.5 IC: Collaboration with commercial parties		
In case of collaboration with commercial/profit organizations, informed consent will be/has been obtained for this type of collaboration		YES
5.4.6 IC: Linking with other registries		
In case the data will be linked with other registries, informed consent will be/has been obtained for this linkage(s)		YES
5.4.7 IC: Incidental findings		
In case there is a risk of incidental findings, informed consent will be/has been obtained to return findings to the participant		YES
Participants are asked (written, consent form) whether they would like to be informed about incidental findings.		
5.4.8 IC: FAIR Data		
In case data collected for the present study will be shared for future studies, informed consent will be obtained for this		YES
5.4.9 IC: other aspects		
NA		
5.4.10 Withdrawal		
• Can participants withdraw informed consent before publication and will all data/ biomaterials of that participant be destroyed		NO
• Does the participant information letter contain information on how to withdraw		YES
If data or biomaterials have already been used, it cannot be destroyed anymore as stated in the consent form.		

## 5.5 Research Data Management Plan (RDMP)

In this study the data will be collected, processed, and archived in accordance with the General Data Protection Regulation (GDPR) and the FAIR (Findable, Accessible, Interoperable, Reusable) principles under the responsibility of the Principal Investigator. A research data management plan (RDMP) has been drawn up to describe the further operational details and procedures.

the RDMP section below is completed  
 a separate RDMP document will be attached to this protocol (appendix)

### 5.5.1 Data collection

• Only essential baseline characteristics and data required to answer the research question(s) will be collected (retrieved from Acutelines)	YES/NO

Primary outcome:            Ultrasound measurement images of the rectus femoris muscle cross-sectional area and data about ED revisit or death within three months and functional decline (Katz ADL-6 survey score or new institutionalization) within twelve months of their ED visit.
 
Secondary and other outcomes:            Data from the APOP questionnaire.
	

• Tooling (eg, software and procedures) used for collecting, processing, analysing, and storing data will be compliant with the UMCG policy and Standard Operating Procedures in the UMCG Research Toolbox.
	

### 5.5.2 Anonymization and pseudonymization

• Data will be anonymised during data collection (i.e. data cannot be linked back to the participant)	NO (only partially)

To allow follow-up of participants through surveys and importing data from the electronic health records or external sources, data cannot be anonymised upon collection in Acutelines, but have to be stored pseudonymized.
	
• Data will be pseudonymized by use of a code list stored in the electronic patient file (EPD) during data collection.	YES
• Indirect and direct identifiable information collected will be minimized and only collected for the purpose of this study	YES
• Direct identifiable information (e.g. contact details, code list/encryption key/subject identification log) will be stored separately from pseudonymized data in the electronic patient files (EPD), while the email address is stored in RedCap (field marked and protected as "identifier").	YES

### 5.5.3 Data access (during the study)

• Direct identifiable information can only be accessed by the Principal Investigator and study delegates after authorization by the Principal Investigator.	YES
• Pseudonymized/anonymized data can only be accessed by the Principal Investigator and study delegates after authorization by the Principal Investigator.	YES
• Data roles, responsibilities, access and authorization - during the study and after study completion - will be managed and documented (e.g. in the RDMP, on study delegation log).	YES

### 5.5.4 Data sharing (during and after study completion)

In case data (and biomaterials) will leave the UMCG, will you contact the loket Contract Research to arrange the proper contracts? ([contact])	NA/YES/NO
--	------------------

In case data (and biomaterials) will leave the UMCG, will you contact the Acutelines steering group and manager to arrange the proper contracts? ([contact])	NA/YES/NO
---	------------------

### 5.5.5 Data storage (during and after study completion)

• Digital data will be archived on the UMCG network complying with strict UMCG security	YES
---	------------

and back-up policy.	
• Paper source data and study files will be archived within the UMCG facilities.	YES
• Source data, study files and digital data will be stored 15 years after the study is completed.	YES
5.5.6 Data re-use and access after completion of the present study ('FAIR data')	
• Data will become available and shared for re-use and participants will be asked informed consent for this ('FAIR data')	YES
Acutelines stimulates re-use and access of data ("FAIR data"), which is the primary aim of Acutelines and for which participants are asked informed consent.	
• Data will be made findable by including the description of the study (and type of data (i.e. metadata) in the UMCG FAIR data catalogue and other discipline specific catalogue(s).	YES
Data and biomaterials are findable through the website (acutelines.umcg.nl), where a data dictionary can be found and a link to the Groningen data catalogue.	
• Review procedure, conditions and agreements for re-use of data and access to data by other researchers will be drawn up.	YES
These are described in the Acutelines Biobank reglement	
• For this study a discipline specific metadata standard will be chosen (i.e. to increase interoperability and re-use).	YES
<if no, explain>	
• All new data derived in this study will be returned to Acutelines to enrich the dataset (i.e. to increase interoperability and re-use).	YES/NO

## 5.6 Management of biomaterials

Will biomaterials be collected, processed, analyzed and/or stored for the purpose of this study	YES
Data and biomaterials are collected as part of Acutelines (de novo biobank)	
5.6.1 Retrospective study (see sections 1, 5.2.2, and 5.4.1)	
If biomaterials will be used from a secondary/further use biobank that has not been approved by the Board of Directors of the UMCG, how will be prohibited that biomaterials necessary for future diagnostic/treatment purposes will be used in the present study.	NA
5.6.2 Biomaterials collection	
• Only biomaterials required to answer the research question(s) will be collected	NO
• What biomaterials will be collected	Plasma (EDTA, Li-Heparin, citrate), buffy coat (EDTA), wholeblood RNA (PAXGene), serum, urine, feces
• How will the biomaterials be collected and processed	Biomaterials are collected and processed according to the procedures as described by Acutelines.
5.6.3 Pseudonymization and access to biomaterials	
• Does the storage unit of the biomaterials comprise information that the participant (in)directly identifies, other than the participant's number and / or the sample number.	NO
• Biomaterials can only be accessed by the Principal Investigator and study delegates after authorization by the Principal Investigator	YES
5.6.4 Sharing of biomaterials (during and after study completion)	
In case biomaterials (and data) will leave the UMCG, will you contact the loket Contract Research to arrange the proper contracts? ([contact])	NA/yes/no
5.6.5 Biomaterials storage (during and after study completion)	
• Where and how will the biomaterials be stored	Biomaterials are collected and stored by Acutelines in the Central Freezer facility UMCG.
• Biomaterials will be stored 15 years after the study is completed	NA
	Biomaterials are collected and stored by Acutelines, for at least 15 years.


 
What will be done with the remaining biomaterials after study completion (eg. destroyed, returned to biobank/previous study, stored) Biomaterials are only collected as part of Acutelines, no extra biomaterials will be collected.
 
	
5.6.6 Biomaterials re-use and access after completion of the present study
 
Note: Acutelines stimulates re-use and access of data ("FAIR data"), which is the primary aim of Acutelines and for which participants are asked informed consent. Data and biomaterials are findable through the website (acutelines.umcg.nl), where a data dictionary can be found and a link to the Groningen data catalogue.
	NA 
--	---	--

## 5.7 Burden, Risks & Benefits

 
If participants are patients: Can be deviated from the standard care / diagnostic procedures (e.g. can medical treatment be postponed or limited)
 
	NA/yes/no 		
Note: burden is minor, data and biomaterials are collected as part of Acutelines.			

 
Will the participants risk any injuries and/or other discomfort when they participate in the proposed study
 
	Yes, minimal risk/burden 	Yes, more than minimal risk/burden 	No 
Note: data and biomaterials are collected as part of Acutelines			

 
Participant benefits/reward/incentives: not applicable.
 
			

## 5.8 Incidental findings

 
Is there a risk of incidental findings?
 
	Yes, minimal risk 	Yes, <math>\geq</math> substantial risk 	No 

If yes,
 
 
In case of incidental findings resulting from the POCUS ultrasound, patients will be referred to radiology at the time of the procedure for formal ultrasonography of their leg, and findings will be fed back to the treating physician
 
The patient will be informed of the need of a formal ultrasonography in case of incidental findings
 
			

## 5.9 Data analysis

 
Justification of sample size (e.g. power analysis)
 

The sample size is calculated based on functional decline and mortality in elderly visiting the ED. We defined functional decline as at least one point increase in the Katz ADL-6 survey score or new institutionalization (higher level of assisted living) within twelve months after ED visit. Prior research in the Netherlands found 9,5% of patients aged <math>\geq 70</math> year died within three months after ED visit and 30,6% experienced functional decline or mortality at 90-day follow-up [8]. With an assumed prevalence of the composed endpoint of 30%, 54 patients are needed to be able to confirm a diagnostic test accuracy with a sensitivity and specificity of <math>>0.8</math> each for a predefined Qcsa cut-off value with a power of 90% and an alfa error of 0.05. To allow for loss of follow-up, 25% more patients will be recruited, resulting in a sample size of 68 patients.

 
Statistical analysis
 

Continuous variables are expressed as mean (95% CI) when normally distributed and median with interquartile range when not normally distributed. Categorical data are presented as absolute

numbers and percentages.

There is a difference in muscle mass between man and woman. The ultrasound measured Qcsa will therefore be adjusted for sex by multiplying female Qcsa with the coefficient 1.484 (male=1) prior to analysis [15]. Diagnostic accuracy of QCSA will be presented as sensitivity and specificity of the optimum Qcsa cut-off point to separate cases (primary endpoint reached after three or twelve months) from non-cases. This optimum cut-off point is calculated as the maximum sum of sensitivity + (1-specificity) using ROC statistics (under the condition of equal costs of misqualification).

A logistic regression model will be used to evaluate whether individual Qcsa predicts functional decline, ED revisit or death. Age, comorbidity, Katz ADL-6, known dementia are defined as clinically relevant covariates and will be included in the regression model.. The predictive ability of the multivariable risk prediction models (e.g. Qcsa prediction model vs APOP prediction model) will be compared.  $\chi^2$  values will be calculated for each prediction model.

A 2-sided P-value <0.05 will be considered statistically significant. Missing data are reported in the results section according to the STROBE 2015 guideline. All statistical analyses will be performed using R or SPSS 26.0 software.

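### The stated 90% power to confirm sensitivity and specificity above 0.8 with 54 patients is unsupported; tested against 0.8, exact power for sensitivity is 6–17% two-sided or 14–35% one-sided (true value 0.90–0.95)

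*Combined protocol and SAP*

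**What the plan says.** All of this stands in section 5.9 (Data analysis).

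- Basis: "The sample size is calculated based on functional decline and mortality in elderly visiting the ED". The cited Dutch study found that "30,6% experienced functional decline or mortality at 90-day follow-up", and the text continues "With an assumed prevalence of the composed endpoint of 30"%.
- Claim: "54 patients are needed to be able to confirm a diagnostic test accuracy with a sensitivity and specificity of" more than 0.8 each, "for a predefined Qcsa cut-off value with a power of 90% and an alfa error of 0.05".
- Inflation: "To allow for loss of follow-up, 25% more patients will be recruited, resulting in a sample size of 68 patients".
- Analysis: "Diagnostic accuracy of QCSA will be presented as sensitivity and specificity of the optimum Qcsa cut-off point". On how that point is found: "This optimum cut-off point is calculated as the maximum sum of sensitivity + (1-specificity) using ROC statistics".

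The sample-size text gives no null value, no assumed true sensitivity or specificity, no test and no sidedness. The end of the section sets a two-sided 0.05 level for the analyses in general. No value for a predefined cut-off appears anywhere in the document. The primary objective in section 4 covers ED revisit or death within three months and functional decline within twelve months.

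**The concern.** A power figure means something only for a stated null and a stated true value, and the plan gives neither. The natural reading of confirming accuracy above 0.8 is a null of 0.8. About 16 cases looked far too few to reject that value for sensitivity with 90% probability.

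The whole sample size rests on this one sentence. Readers and approvers will take the study as 90% assured of showing sensitivity and specificity above 0.8. They may also read a disappointing result as evidence against the measurement, when the study was too small to show the claim either way.

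**Working it through.** **Inputs from section 5.9:** N = 54 evaluable (68 recruited), prevalence 30%, target above 0.8 for each measure, power 90%, alpha 0.05. **Assumed, because the plan gives none:** the null, the true values and the test. Upper-tail level is 0.025 (two-sided) or 0.05 (one-sided).

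**1. The plan's own figures.** 54 × 1.25 = 67.5, so 68: reproduced. Expected cases are 54 × 0.30 = 16.2 (68 × 0.30 = 20.4). The 54 does not follow from the stated inputs alone, but at least two recipes lead to it. Both are guesses at the source.

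- Wald formula for sensitivity alone, null 0.5, expected 0.8, one-sided: (1.645 + 1.282)² × 0.16 / 0.09 = 15.2, so 16 cases; 16 / 0.30 = 53.3, so 54 patients. The two-sided version gives 18.7, so 19 cases and 64 patients.
- 95% half-width of 0.20 around 0.8: 1.96² × 0.16 / 0.04 = 15.4, so 16 cases and 54 patients.

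The first concerns accuracy above 0.5. The second is a precision calculation with no power in it.

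**2. Null 0.8 with exactly 16 cases.** Even 16/16 is not enough for the exact two-sided test: 0.8¹⁶ = 0.028 > 0.025, and the exact 95% lower limit is 0.794. One-sided, 16/16 is required, with probability 0.9¹⁶ = 0.185 or 0.95¹⁶ = 0.440.

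**3. Null 0.8, averaged over a Binomial(N, 0.30) number of cases.** Each cell gives two-sided / one-sided power.

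| | True 0.90 | True 0.95 |
|---|---|---|
| Sensitivity, exact, N = 54 | 6% / 14% | 17% / 35% |
| Sensitivity, exact, N = 68 | 11% / 20% | 32% / 48% |
| Both measures, exact, N = 54 | 2% / 6% | 12% / 29% |
| Sensitivity, mid-P, N = 54 | 14% / 24% | 34% / 51% |
| Sensitivity, score, N = 54 | 9% / 22% | 23% / 48% |
| Sensitivity, Wald, N = 54 | 40% / 48% | 70% / 78% |

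For both measures, power is the product of the two given the case count. No test reaches 90%. The Wald figures are inflated: one-sided with 16 cases it rejects at 15/16, where its actual error is 14%.

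For scale only, 90% exact power for sensitivity against 0.8 needs about 112–149 cases at true 0.90 (374–497 patients at 30%), or 44–55 cases at true 0.95 (147–184 patients).

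**4. Null 0.5, true value 0.80, both measures, averaged in the same way.**

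| | N = 54 | N = 68 |
|---|---|---|
| Exact | 60% / 74% | 74% / 84% |
| Mid-P, score, Wald | 69–78% / 81–84% | 80–85% / 88–90% |

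With exactly 16 cases, all four tests one-sided need 12/16 for sensitivity and have 80% power. So the first recipe in step 1 does not deliver its nominal 90% either.

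**5. What the size does support (exact 95% intervals, cut-off fixed in advance).**

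| | 54 evaluable | 68 evaluable |
|---|---|---|
| Sensitivity, 30% prevalence | 13/16: 0.54–0.96 | 16/20: 0.56–0.94 |
| Specificity, 30% prevalence | 30/38: 0.63–0.90 | 38/48: 0.65–0.90 |
| Either, 50% prevalence (assumption) | 22/27: 0.62–0.94 | 27/34: 0.62–0.91 |

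**6. Consistency of the text.** The calculation is for a cut-off set beforehand, while the analysis reports accuracy at an optimum found in the same patients. These are different quantities, and the second is optimistic. The 30% follows a 90-day rate of functional decline or mortality, but the primary objective adds ED revisit and extends decline to twelve months. The true prevalence may therefore differ.

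**The case against.** The best defence is that 0.8 was the expected performance and not the null. The null of 0.8 and the true values of 0.90–0.95 are this review's assumptions, and other undocumented nulls make 16 cases adequate for sensitivity at an expected 0.8: the exact test has 91.8% power against 0.40 two-sided or 0.45 one-sided. Against 0.5, 90% is also within reach under kinder settings. With 54 patients, exact power for both measures is 79% / 88% (two- / one-sided) at true 0.85, 92% / 96% at true 0.90, and 90% / 95% at true 0.85 with 40% prevalence. With 68 evaluable and true 0.80, the one-sided Wald test just reaches 90% at 30% prevalence, and the exact one-sided test gives 92% at 40%. The exact test is also conservative: for sensitivity against 0.8 at a true value of 1.0 with 54 patients, it gives 46% / 79%, where the other three give 96–100% one-sided.

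This stands in part. The 54 is not shown to be an arithmetic slip, and a coherent calculation may lie behind it. But every such route shows accuracy above about 0.4 to 0.5, and the sentence claims above 0.8.

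It can also be said that no test of sensitivity or specificity is planned, that the study is observational with minor burden, and that only wording would change. That is why no larger sample is asked for. It does not make the stated 90% true, and that figure is the only justification of the study's size.

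**Conclusion.** The concern holds. As written, the 90% cannot be verified, and on the plain reading (null 0.8) it is far from met: 6–17% two-sided or 14–35% one-sided for sensitivity alone with 54 patients, and 2–12% or 6–29% for both measures. These figures rest on the exact test, 30% prevalence, a random case count and assumed true values of 0.90–0.95. The conclusion does not depend on the choice of test, since none of the four exceeds 78% in that range with 54 patients. More cases do not rescue it either: with 68 evaluable, 60% prevalence and true sensitivity 0.95, exact power is 77% two-sided and 86% one-sided. The study can estimate sensitivity to within roughly 0.55–0.95 if it is near 0.8; it cannot be expected to confirm that it exceeds 0.8. The sentence must be corrected.

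**What to change.** Keep 68 patients. In section 5.9, delete the claim of 90% power to confirm values above 0.8. Make the sample-size text and the analysis refer to the same cut-off: either drop the mention of a predefined value, or state that value and also report accuracy at it. Suggested replacement:

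> The sample size is justified by precision. With 54–68 evaluable patients and an assumed prevalence of 30% (16–20 cases, 38–48 non-cases), an observed sensitivity near 0.8 has an exact 95% CI of about 0.55–0.95 and an observed specificity near 0.8 about 0.63–0.90; at 50% prevalence (assumption) both are about 0.62 to 0.91–0.94. These intervals apply to a cut-off fixed in advance. The analysis uses an optimum cut-off derived from the same data, so its estimates will be optimistic and these intervals take no account of that choice. The 30% comes from a 90-day rate of functional decline or mortality, not from the composite of this study.

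If a predefined cut-off is stated and reported, adapt the sentence on the optimum cut-off accordingly. If the authors prefer to keep a power statement, it should give their own null, true value, sidedness and test. For example: exact test, null 0.5, true sensitivity and specificity 0.80, 30% prevalence; power for both measures 60–74% two-sided or 74–84% one-sided with 54–68 patients.

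The cost is wording in one section, with no extra patients or data. Keeping a predefined cut-off adds one more reported sensitivity and specificity. The downside is a less favourable stated figure.

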POCUS has been shown to be a promising technique to measure skeletal muscle mass [12]. It is non-invasive, can be performed at the bedside and has an excellent intra-class correlation coefficient for intra- and inter-observer agreement. [13, 14] Recent studies in a subgroup of hospitalized patients have shown that Qcsa measurements can predict readmission and mortality [15, 16]. ED data however are scarce: Shah et al found in a subset of elderly trauma patients that ultrasound measurements of biceps and quadriceps had modest concordance with the Clinical Frailty Scale (CFS9) [17], whereas Benton et al demonstrated that ultrasound measurements of sarcopenia in older non-trauma patients were (to a variable extend) associated with frailty, falls and subsequent hospitalizations [18].

As POCUS measurement of Qcsa is independent of patient effort and functional or cognitive impairment, it has the potential to be a valuable (alternative) screening tool for functional decline

and mortality in older patients in the ED. However, until now, no data have been published about the relation between Qcsa and functional outcome for patients presenting in the ED.

The aim of this study is to evaluate whether ultrasound measurements of the Qcsa in the ED may be utilized to identify older patients who are at risk for functional decline, ED revisit or death. Our study hypothesis is that Qcsa measurements can predict functional decline, ED revisit or death of older ED patients.

- **Research question**

Primary objective

To evaluate:

- The relation between POCUS measurements of the Qcsa in patients >70 presenting in the ED and ED revisit or death within three months and functional decline within twelve months of their ED visit. Functional decline in this respect is defined as at least one point increase in the Katz ADL-6 survey score or new institutionalization (higher level of assisted living) within twelve months after ED visit.

Secondary objectives

To evaluate:

- To compare the ability of the Qcsa ultrasound to predict functional decline, ED revisit or death in older patients in the ED to the APOP questionnaire (gold standard).
- To compare the added value of Qcsa ultrasound to the APOP questionnaire in the prediction of functional decline, ED revisit or death in older patients in the ED.
- To evaluate the relation between Qcsa ultrasound and physical activity (as scored by KATZ ADL-6 questionnaire).

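### The sample size claims 90% power to confirm accuracy at a predefined Qcsa cut-off, but none is given; the plan picks the cut-off and reports its accuracy in the same patients, uncorrected

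*Combined protocol and SAP*

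**What the plan says.** The two relevant paragraphs stand next to each other in section 5.9 (Data analysis).

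- **Justification of sample size.** At an assumed 30% prevalence of the composite endpoint, "54 patients are needed to be able to confirm a diagnostic test accuracy with a sensitivity and specificity of" more than 0.8, "each for a predefined Qcsa cut-off value with a power of 90% and an alfa error of 0.05". Adding 25% for loss to follow-up gives 68.
- **Statistical analysis.** "Diagnostic accuracy of QCSA will be presented as sensitivity and specificity of the optimum Qcsa cut-off point". The next sentence explains where that point comes from: "This optimum cut-off point is calculated as the maximum sum of sensitivity + (1-specificity) using ROC statistics". Separately, "A logistic regression model will be used to evaluate whether individual Qcsa predicts functional decline, ED revisit or death", with age, comorbidity, Katz ADL-6 and known dementia as covariates.

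The protocol gives no numeric Qcsa cut-off and no source for one. The only constant carried over from a cited study is the sex coefficient 1.484, which rescales the measurement and is not a threshold. There is one single-centre cohort of 68 (sections 5.2 and 5.3). The plan mentions no validation sample, bootstrap, cross-validation, confidence interval for sensitivity or specificity, or test against 0.8.

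**The concern.** A cut-off cannot be both fixed in advance and calculated from the study's ROC curve. The sample-size paragraph describes a confirmatory test at a known threshold; the analysis paragraph describes a search for the best threshold. Choosing the threshold that maximises accuracy and then quoting accuracy in the same patients gives estimates that are too high on average, and with about 16 cases the excess is not negligible.

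Sensitivity and specificity are the quantities on which the study was sized, and the ones a reader would use to judge Qcsa as a screen when a questionnaire is not possible. If the plan is followed as written, they will look better than the chosen cut-off would perform in new patients. They also cannot be read as confirmation of more than 0.8 on both.

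**Working it through.** **1. The plan's own figures.** 54 × 1.25 = 67.5, rounded up to 68, which agrees. The 54 cannot be reproduced uniquely because no null value is stated. One variant that gives it assumes a null of 0.5, a true value of 0.8, one-sided 0.05, 90% power and variance under the alternative:

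cases = (1.645 + 1.282)² × 0.8 × 0.2 / 0.3² = 15.2, so 16; 16 / 0.30 = 53.3, so 54.

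The same formula with two-sided 0.05 gives 18.7, so 19 cases; 19 / 0.30 = 63.3, so 64 patients. If confirming more than 0.8 meant a null of 0.8, even 16 of 16 would give only a one-sided p of 0.8¹⁶ = 0.028. So 54 is not shown to be miscalculated, but every one of these derivations applies only to a cut-off fixed in advance.

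**2. Cost of selecting the cut-off.** Inputs from section 5.9: N = 54 and prevalence 30%, so 16 cases and 38 non-cases. Assumptions: a normally distributed marker with equal variance in cases and non-cases, and a cut-off maximising sensitivity + specificity − 1 (Youden index J). With separation d = √2 Φ⁻¹(AUC), the best fixed cut-off has sensitivity = specificity = Φ(d/2). Means over simulated studies, as sensitivity/specificity:

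| AUC | Best fixed cut-off | Reported at selected cut-off | True at selected cut-off | J reported | J true |
|---|---|---|---|---|---|
| 0.70 | 0.645/0.645 | 0.725/0.679 | 0.623/0.637 | 0.404 | 0.260 |
| 0.883 | 0.80/0.80 | 0.855/0.827 | 0.776/0.795 | 0.682 | 0.571 |

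- Excess at AUC 0.70: 0.725 − 0.623 = 0.102 (sensitivity) and 0.679 − 0.637 = 0.042 (specificity).
- Excess at AUC 0.883: 0.855 − 0.776 = 0.079 and 0.827 − 0.795 = 0.032. Against the best fixed cut-off it is about 5 and 3 points.
- An uninformative marker (AUC 0.50) averages a reported J of 0.17 when the truth is 0. That is well short of the target, so the procedure would not make a useless marker look adequate.
- Over 20% to 50% prevalence at N = 54, the sensitivity excess runs from 13 down to 6 points (AUC 0.70) and from 10 down to 5 points (AUC 0.883).

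**3. Chance that both reported values exceed 0.8.**

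Fixed cut-off, true 0.80/0.80, N = 54: P(at least 13 of 16) × P(at least 31 of 38) = 0.598 × 0.500 = 0.30. With the selected cut-off the simulation gives 0.43. When the best true values are about 0.72/0.72, the chances are 4% (fixed) and 11% (selected).

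With 68 patients (20 cases, 48 non-cases) the strict rule gives 21% against 31%, and 2% against 5%. The fall from N = 54 is a rounding effect: 16/20 is exactly 0.80 and fails a strict inequality. Counting 0.80 as a pass, the first pair becomes about 31% against 43 to 44%.

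**4. Attainable precision.** Exact (Clopper-Pearson) 95% intervals for a fixed cut-off, which is the best case:

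| Patients | Sensitivity | Specificity |
|---|---|---|
| 54 | 13/16 = 0.81 (0.54–0.96) | 31/38 = 0.82 (0.66–0.92) |
| 68 | 16/20 = 0.80 (0.56–0.94) | 39/48 = 0.81 (0.67–0.91) |

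Hanley–McNeil at AUC A = 0.70: Q1 = 0.70/1.30 = 0.538 and Q2 = 0.98/1.70 = 0.576. For 16/38, SE² = [0.21 + 15(0.538 − 0.49) + 37(0.576 − 0.49)] / 608, about 0.0068, so the 95% half-width is about 0.16. For 20/48 it is about 0.14.

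**5. Which correction works.** Mean J at 16/38, from 1,500 simulated datasets with 200 resamples each:

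| AUC | Reported | Simple bootstrap | Out-of-bag | 10-fold CV | True |
|---|---|---|---|---|---|
| 0.50 | 0.166 | 0.063 | −0.002 | −0.002 | 0.000 |
| 0.70 | 0.404 | 0.312 | 0.249 | 0.258 | 0.260 |
| 0.883 | 0.683 | 0.613 | 0.558 | 0.569 | 0.573 |

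Simple optimism subtraction removes (0.404 − 0.312) / (0.404 − 0.260) = 64% of the excess at AUC 0.70, and 62% and 64% in the other two rows. The other two methods come within 0.02 of the truth.

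**The case against.** - **The regression is the real test.** Section 4 states: "Our study hypothesis is that Qcsa measurements can predict functional decline, ED revisit or death of older ED patients". The logistic model addresses that hypothesis without a cut-off. This stands and limits the severity, but the regression does not correct the sensitivity and specificity, and it is not what the study was sized on.
- **The plan sets no pass mark.** The analysis paragraph only presents accuracy; the language of confirmation appears solely in the sample-size paragraph. This is fair, so the percentages in step 3 describe how a reader may take the results and not a planned decision rule.
- **The simulated criterion is not the printed one.** The printed sum, sensitivity + (1 − specificity), is largest when every patient is classed positive, and the simulated figures would not apply to it. They assume that the Youden index was meant. The misprint is a separate point.
- **The prevalence may exceed 30%.** The cited 30.6% covers functional decline or death at 90 days, whereas the primary objective adds ED revisit and follows decline to twelve months. With more cases the excess in sensitivity shrinks, to 5 or 6 points at 50%, but does not vanish.
- **Silence is not proof of omission.** True, in a short investigator-initiated protocol. Yet there is only one cohort, and nothing points to a correction.
- **The bias is small beside the sampling error.** At the target accuracy, 5 and 3 points are modest against an interval of 0.54 to 0.96. But the bias has a known direction, and the plan reports no interval that would show the uncertainty either.

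**Conclusion.** The concern holds. The stated 90% power belongs to an analysis at a fixed cut-off that the plan neither specifies nor performs, and the accuracy it does report will be optimistic on average. At N = 54 and 30% prevalence the Youden index is overstated by about 0.11 (AUC 0.883) to 0.14 (AUC 0.70).

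The upward direction follows from maximising and assessing accuracy in the same data. The size rests on the binormal model, the Youden reading of the criterion and the assumed number of cases. That the same patients are used without correction is inferred from the single cohort and from the absence of any validation step. The point should be put right before analysis, but it does not undermine recruitment, data collection or the regression.

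**What to change.** **Main route.** Keep the data-derived cut-off and call it exploratory. Report the AUC with its 95% CI, and internally validated sensitivity and specificity with 95% CIs, re-selecting the cut-off in every resample. Name the method in advance. Scoring each bootstrap cut-off in the left-out patients, or repeated stratified 10-fold cross-validation, is preferable to simple optimism subtraction. That preference rests on one binormal simulation; the essential element is re-selection inside the resampling. Reword the sample-size paragraph so that it no longer claims power to confirm accuracy at a predefined cut-off, and state the expected precision instead, using the intervals in step 4 as the best case.

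**Alternative.** If a sourced, sex-adjusted cut-off exists, write it into the protocol before outcomes are seen and report sensitivity and specificity at that value with exact 95% CIs. The documents contain no such value, so it would have to be found.

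**Cost.** Protocol wording, a restated sample-size rationale and a short script in R, which section 5.9 already allows. No extra patients, visits or procedures are needed. The price is accuracy figures that look less favourable.
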